3.1 Screening

Prior to entry into the study, patients presenting with acute stroke symptoms will be screened to determine if they meet the inclusion and exclusion criteria for entry into the study. Patients who are found to be ineligible for entry into the study will be excused from further participation. Patients who are eligible for the study will review and sign (or have a legally authorized representative review and sign) the Patient Information and Consent form prior to enrollment into the study. All patients enrolled will be blinded to treatment allocation and monitored throughout the required follow-up period.

3.2 Pre-Procedure (Admission) Evaluations

3.2.1 Obtain patient medical and therapeutic history.

3.2.2 Females of childbearing potential must have a pregnancy test.

3.2.3 Exclude all patients who are not eligible and record the reason in the screening log.

3.2.4 Perform admission NCCT scans, physical examination, neurological and functional examinations, and serum chemistries. Physical examination will include recording of supine blood pressure and heart rate. Serum chemistry will include blood urea nitrogen (BUN), creatinine, complete blood count (CBC) plus platelets, and international normalized ratio (INR), prothrombin time (PT) / partial thromboplastin time (PTT).

3.3 Enrollment

Each center will have two roll-in cases prior to actual enrollment. These patients will not be part of the trial but will be followed for 90 days for safety. Prior to enrollment into the study, each patient will undergo an angiographic determination of the suspected vascular occlusion. Perform an arterial access procedure using standard percutaneous technique.

Perform a digital subtraction angiography (DSA) to define the angio-architecture of the occluded vascular segment. While a DSA to define the angio-architecture of the occluded vascular segment is preferred, CTA or MRA is an acceptable substitute. When possible, an assessment of collateral blood flow by DSA should be done per institutional standard of care, particularly in cases of terminal internal carotid artery occlusion.

If the occlusion is in a treatable vessel, position an appropriate guide catheter and advance the Penumbra Reperfusion Catheter into the occluded target vessel and the patient will be randomized to one of the following arms:

- 1) The Penumbra Separator 3D with the Penumbra System, or
- 2) The Penumbra System without the Separator 3D.

The randomization code will be obtained from a system provided by a vendor. A patient is considered enrolled once a treatment arm is assigned from the randomization system.

All patients will be assessed for a period of 90 days from randomization.

Randomized patients who were excluded for angiographic reasons will be followed for 90 days. The reasons for not including these patients will be captured in the Case Report Forms.

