2.3.2 Exclusion Criteria

- History of stroke in the past 3 months
- Females who are pregnant
- Pre-existing neurological or psychiatric disease that could confound the study results such as a pre-stroke mRS score ≥ 1
- Known severe allergy to contrast media
- Uncontrolled hypertension (defined as systolic blood pressure > 185 mmHg or diastolic blood pressure > 110 mmHg)
- CT evidence of the following conditions at randomization:
 - Significant mass effect with midline shift
 - Large infarct region $> 1/3$ of the middle cerebral artery territory
 - Evidence of intracranial hemorrhage
- Angiographic evidence of an arterial stenosis proximal to the occlusion that could prevent thrombus removal
- Angiographic evidence of preexisting arterial injury
- Rapidly improving neurological status prior to enrollment
- Bilateral stroke
- Intracranial tumors
- Known history of cerebral aneurysm or arteriovenous malformation
- Known hemorrhagic diathesis, coagulation deficiency, or on anticoagulant therapy with an International Normalized Ratio (INR) of > 1.7
- Baseline platelets $< 50,000$
- Use of IV heparin in the past 48 hours with PTT > 1.5 times the normalized ratio
- Baseline glucose < 50 mg/dL or > 300 mg/dL
- Life expectancy less than 90 days prior to stroke onset

- Participation in another clinical investigation that could confound the evaluation of the study device

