3.8 Angiographic Imaging

At screening, perform a DSA to define the angio-architecture of the occluded vascular segment. While a DSA to define the angio-architecture of the occluded vascular segment is preferred, CTA or MRA is an acceptable substitute.

When possible, an assessment of collateral blood flow by DSA should be done per institutional standard of care, particularly in cases of terminal internal carotid artery occlusion.

Prior to mechanical thrombectomy by the Penumbra Device, obtain a baseline TIMI/TICI scores by DSA. CTA or MRA is not an acceptable substitute for this assessment. The investigator shall make an initial assessment of TIMI/TICI flow in the target vessel territory.

TIMI/TICI scores are to be assessed after completion of the procedure by the Separator 3D. If necessary, other components of the Penumbra System can be used at the discretion of the investigator with the TIMI/TICI scores recorded before and after each use. In the event that adjunctive treatments were used, TIMI/TICI scores should be assessed and recorded before and after each treatment. The TIMI/TICI scores after the use of the Penumbra System as well as after adjunctive treatments will be used for analysis.

Pre-procedure and post-procedure angiograms shall be sent to an unbiased Core Laboratory blinded to treatment allocation to make a final determination on TIMI/TICI flow.

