3.4 Blinding

The Penumbra Inc. clinical team responsible for the conduct of the study, the investigator, and center study personnel will not be blinded to each patient's randomized treatment group throughout the course of the study. The study subjects and the Core Laboratory will be blinded to treatment assignment.

4 Interim Analysis

No interim analyses are planned for the purpose of stopping the study early.

5 Analysis Populations

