9.1 Primary Effectiveness Analysis

The primary effectiveness variable is the proportion of patients with a post procedure TICl score of 2 to 3. The proportion of patients in each group who are successful based on this criterion will be calculated. The Core Laboratory data supersede the investigator-reported data in all analyses of TICl scoring.

For those patients who are treated with IA tPA or other non-FDA-approved treatments for the purpose of reducing the clot burden, their TICl score will be analyzed as a treatment failure (i.e. TICl 0 to 1) for the primary effectiveness analysis.

The primary effectiveness analysis will be the difference between the Penumbra System only group (control) and the Penumbra System with Separator 3D group. A binomial comparison will be used to test the one-sided null hypothesis that the difference in proportions is less than or equal to -0.15 ($H_0: P_{3D} - P_{Control} \leq -0.15$) vs. the alternative ($H_1: P_{3D} - P_{Control} > -0.15$). This is equivalent to evaluating that the lower bound of the 90% confidence interval for the difference is above 15%. The primary effectiveness analysis will be performed on the Per Protocol (PP) subject population. The analysis based on the Intent-To-Treat (ITT) population will be considered as supportive.

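### Angiographic ineligibility can surface after the unblinded operator knows the arm, and such patients drop out of the per-protocol set that decides success; the bias is possible, in either direction, and cheap to prevent.

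*Protocol*

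**What the plan says.** Protocol 3.3 fixes the moment of enrolment: "A patient is considered enrolled once a treatment arm is assigned from the randomization system". By then arterial access has been made and the Reperfusion Catheter advanced into the target vessel. The same section then says: "Randomized patients who were excluded for angiographic reasons will be followed for 90 days", and adds "The reasons for not including these patients will be captured in the Case Report Forms". It gives no list of qualifying reasons, no time limit and no named assessor.

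On imaging before randomisation, Protocol 3.3 states: "While a DSA to define the angio-architecture of the occluded vascular segment is preferred, CTA or MRA is an acceptable substitute". Protocol 3.8 does not accept CTA or MRA for the baseline flow score, but times that score against treatment and not against randomisation: "Prior to mechanical thrombectomy by the Penumbra Device, obtain a baseline TIMI/TICI scores by DSA".

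Protocol 2.3.2 lists two angiographic exclusion criteria. One is pre-existing arterial injury. The other is "Angiographic evidence of an arterial stenosis proximal to the occlusion that could prevent thrombus removal".

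SAP 3.4 states that "the investigator, and center study personnel will not be blinded to each patient's randomized treatment group"; only patients and the core laboratory are blinded. SAP 5.1 puts every consented, randomised patient in ITT. It limits PP to patients who received the assigned treatment and had no major violation, without defining major. SAP 9.1 says: "The primary effectiveness analysis will be performed on the Per Protocol (PP) subject population", with ITT supportive. SAP 2 rests study success on the primary non-inferiority criterion alone.

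**The concern.** Taken together, these sections leave a narrow route by which a randomised patient can be judged angiographically unsuitable after the arm is known. Such a patient is not treated, so cannot be in PP, and therefore does not count in the analysis that decides the trial.

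The grounds for exclusion need not be independent of the endpoint: the stenosis criterion is itself a forecast that the clot may not come out. If would-be failures leave one arm more often than the other, the PP comparison is no longer the randomised one. Excess loss from the 3D arm makes a false claim of non-inferiority more likely. Excess loss from control makes it less likely.

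**Working it through.** **Inputs.** From Protocol 9.1 and SAP 3.1–3.2: success 0.80 in both arms, margin 0.15, one-sided alpha 0.05, 103 per group, 115 after 10% attrition, and a normal-approximation confidence bound. Assumed, because the documents do not give them: the share e of an arm that is excluded, and the share f of those excluded who would have failed.

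**The plan's own figure.** Standard error = √(2 × 0.80 × 0.20 / 103) = 0.0557. Power = Φ(0.15/0.0557 − 1.645) = Φ(1.046) = 0.852, as in the SAP. 103/0.90 = 114.4, rounded up to 115. The sample-size arithmetic is sound.

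**Decision rule.** Declare non-inferiority if a − b − 1.645 × √(a(1−a)/n₃ + b(1−b)/n_c) > −0.15. Here a and b are the observed PP success rates in the 3D and control arms, and n₃ and n_c are the PP numbers. Exact binomial enumeration of this rule gives power 0.852 at 103 per arm. With true rates 0.65 and 0.80 and 115 per arm, it gives a false-success probability of 0.050.

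**Effect of exclusion.** PP rate = (p − e(1−f))/(1−e), which is p/(1−e) when all those excluded would have failed (f = 1). For the 3D arm at p = 0.65:
- e = 2%: 0.65/0.98 = 0.663
- e = 3%: 0.65/0.97 = 0.670
- e = 5%: 0.65/0.95 = 0.684

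These shares are 2.3, 3.5 and 5.8 of 115 patients. Against a control rate of 0.80, the apparent difference moves from −15.0 points to −13.7, −13.0 and −11.6. The PP number in an affected arm is 115(1−e), rounded to 113, 112 and 109.

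False-success probability at true rates 0.65 v 0.80 (nominal 0.05):

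| Who is lost | 2% | 3% | 5% |
|---|---|---|---|
| 3D arm only, all failures | 0.079 | 0.097 | 0.147 |
| 3D arm only, 80% failures | 0.069 | 0.080 | 0.109 |
| Both arms equally, all failures | 0.045 | 0.043 | 0.039 |
| Control arm only, all failures | 0.026 | 0.019 | 0.008 |
| Unrelated to outcome | about 0.05 | about 0.05 | about 0.05 |

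At 10% of the 3D arm, which is the plan's whole attrition allowance, the first row reaches about 0.35. With 10% lost from 3D and 5% from control, all failures, it is about 0.137.

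**The case against.** Much of the protection is already intended. SAP 3.3 randomises only patients who meet the criteria and have finished pre-randomisation screening. Protocol 3.1 screens before entry, Protocol 3.3 asks for an angiographic determination before enrolment, and Table 7 puts the DSA-based flow score under baseline. This stands, and it makes the gap narrow: what is missing is an explicit statement that the DSA and its eligibility reading come before the code.

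The stenosis route is weak. With the catheter already in the target vessel when the code is requested, a blocking proximal stenosis should usually have shown itself. This also stands and suggests small numbers, although the table shows that two or three patients lost from one arm are enough to matter.

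A reader might infer that Protocol 3.3 licenses the operator to exclude patients after allocation. It does not: the sentence is a duty to follow up and record. That the unblinded operator decides is an inference from SAP 3.4, and that the patients leave the deciding analysis follows from SAP 5.1 and 9.1.

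Both listed criteria are neutral between arms, so nothing shows that loss would be unequal. Equally, 3.3 does not confine angiographic reasons to those two criteria. Protocol 1 says the Separator 3D fits catheters of at least 0.041 inch distal inner diameter, while Table 5 pairs it with 032/3MAX (0.032 and 0.035 inch in Table 3) for vessels of 2.5 to 3.0 mm. Those passages need reconciling; meanwhile equal loss cannot be taken for granted.

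ITT keeps everyone, both sets are analysed and disposition is reported. That makes unequal exclusion visible but does not change which analysis decides success.

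**Conclusion.** The point holds as a gap in the ordering of steps and in the PP rule. It does not show that the trial is biased. A reader might infer that the plan favours the 3D arm; the documents do not support this, because they give neither an exclusion rate nor evidence that exclusions would differ by arm. Losing failures from the 3D arm alone at 2 to 5% raises the false-success probability from 0.05 to between 0.079 and 0.147. Equal loss or control-only loss lowers it, and outcome-neutral loss does nothing.

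These figures rest on assumed exclusion shares, true rates at the non-inferiority boundary, and no other attrition. The change is worth making because very few patients can move the error rate and prevention costs little.

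**What to change.** 1. **Protocol 3.3 and 3.8.** Require the baseline DSA, the baseline TICI reading and all angiographic eligibility checks to be completed and recorded before the randomisation code is requested.
2. **Protocol 3.3.** Keep the 90-day follow-up and the recording of reasons; deleting that text would make late exclusions less visible. Add that these exclusions are reported by arm.
3. **SAP 5.1.** Let a randomised patient leave PP for angiographic ineligibility only if the blinded core lab confirms it on the pre-procedure angiogram it already receives, under one rule for both arms. Otherwise keep the patient in the primary analysis, scored as a failure if there is no post-procedure TICI. At present the only provision for such a patient is in the sensitivity analyses of SAP 12.

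**Cost.** Wording, plus a few more screen failures. The DSA is already mandatory and access already made, so no procedure is added. Success rates fall slightly if unconfirmed exclusions count as failures. If exclusion is unrelated to outcome and every excluded patient is scored a failure, 5% in both arms gives 0.80 × 0.95 = 0.76 and 10% gives 0.80 × 0.90 = 0.72. By the same normal approximation, power with 115 analysed per arm is then 84.6% and 81.3%, against 88.5% with none excluded. Restoring 85% would take 117 and 129 analysed per arm. If those excluded would have failed anyway, scoring them as failures does not lower the success rate below that of all randomised patients. The SAP part can be adopted at any time before database lock.

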3.4 Procedure Preparation for the Penumbra System

Procedure should be consistent with those listed in the *Instructions For Use* for each device. Refer to Warnings, Precautions, and Potential Adverse Events in the *Instructions For Use* for each device prior to use. However, for the purpose of this study, the Penumbra Separator 3D System should be used first for the revascularization of the target vessel if the patient was randomized to the Penumbra Separator 3D arm, to be followed by other components of the Penumbra System if necessary at the discretion of the investigators. The exception is the use of the 054 or 041 separators in the Separator 3D arm. Use of these devices in this arm will be considered a protocol deviation. Similarly, use of the Separator 3D in the control arm will be considered a protocol deviation.

- 3.4.1 As each device of the Penumbra System is used, remove the device from the packaging, and inspect for damage or for kinks.
- 3.4.2 Prepare Penumbra System devices for use by flushing the packaging hoop and device with heparinized saline (includes Penumbra Reperfusion Catheter and Penumbra Separator only).
- 3.4.3 Prepare a guide catheter or long femoral sheath according to the manufacturer's *Instructions for Use*.
- 3.4.4 Place the guide catheter or long femoral sheath into the appropriate cerebral artery that is proximal to the thrombus occlusion site.

3.5 Penumbra Reperfusion Catheter Preparation and Use

- 3.5.1 Confirm vessel diameter, and select an appropriate size Penumbra Reperfusion Catheter per the *Instructions for Use*.
 - 3.5.2 The Penumbra Reperfusion Catheter tip may be shaped using the steam shaping mandrel provided.
 - 3.5.3 Attach the rotating hemostasis valve provided to the Penumbra Reperfusion Catheter.
 - 3.5.4 Insert the Penumbra Reperfusion Catheter into a rotating hemostasis valve connected to the proximal hub of a guide catheter. If a guide catheter is not used, insert the Penumbra Reperfusion Catheter through the valve of the long femoral sheath using the peelable sheath. After inserting the Penumbra Reperfusion Catheter, remove the peelable sheath from the vascular sheath, and peel from the Penumbra Reperfusion Catheter Shaft.
 - 3.5.5 Using conventional catheterization techniques under fluoroscope guidance advance the Penumbra Reperfusion Catheter into the target vessel over an appropriate neurovascular guidewire. Position the Penumbra Reperfusion Catheter proximal to the thrombus. Remove the guidewire from the Penumbra Reperfusion Catheter.
- 3.6 Penumbra Separator 3D Preparation and Use
- 3.6.1 For the purpose of this study, the Penumbra Separator 3D System should be used first for the revascularization of the target vessel, to be followed by other components of the Penumbra System at the discretion of the investigators.
 - 3.6.2 Attach the Penumbra Aspiration Tubing to the Aspiration Pump and turn on the Aspiration Pump (Refer to the Aspiration Pump Operation Manual). Allow the Aspiration Pump to run for at least one minute prior to use, and confirm that the Aspiration gauge reads –20inHg. Ensure the valve on the Penumbra Aspiration Tubing is switched to the OFF position.
 - 3.6.3 Penumbra Separator 3D is offered in one size and is designed to fit into the listed Penumbra Reperfusion Catheters (see **Table 5**).

[figure not shown]
Table 5 -- Separator-3D / Reperfusion Catheter Device Sizes

Vessel Size (mm)	Reperfusion Catheters for the Separator-3D
2.5 to 3.0	032 / 3MAX
3.0 – 4.0	041 / 4MAX
>4.0	054 / 5MAX

[figure not shown]
3.6.4 Advance the Penumbra Reperfusion Catheter to gently penetrate the thrombus.

NOTE: Access to the site of occlusion may be aided by the triaxial use of a compatible inner microcatheter of 0.025" ID or greater.

3.6.5 Using the introducer sheath provided, insert the Penumbra Separator 3D through the rotating hemostasis valve and into the proximal hub of the Penumbra Reperfusion Catheter or triaxial microcatheter.

3.6.7 Advance the 3D delivery catheter to the distal edge of the thrombus, then unsheath the Penumbra Separator 3D. To begin aspiration, open the valve on the Penumbra Aspiration Tubing to the ON position. Retract the Penumbra Separator 3D to assist with aspiration and retrieval of the thrombus as shown in **Figure 3**. If necessary, the entire thrombus can be

3.6.8 To stop aspiration, switch the valve on the Penumbra Aspiration Tubing to the OFF position, and turn off the Aspiration Pump.

[figure not shown]
- 3.6.9 Remove the Penumbra Separator 3D.
 - 3.6.10 If necessary, additional Penumbra Separators, Penumbra Separator 3Ds, and Reperfusion Catheters may be used to further remove thrombus at the discretion of the physician.
 - 3.6.11 Using a 5cc or 10cc syringe, aspirate approximately 5cc of blood from the Penumbra Reperfusion Catheter to remove any thrombus that may remain in the catheter.
 - 3.6.12 Obtain a post-treatment angiogram by injecting contrast media through the guide catheter.
- 3.7 Penumbra Separator Preparation and Use
- 3.7.1 Attach the Penumbra Aspiration Tubing to the Aspiration Pump and turn on the Aspiration Pump (refer to the Aspiration Pump *Operation, Service, and Maintenance Manual*). Allow the Aspiration Pump to run for at least one minute prior to use, and confirm that the Aspiration gauge reads –20inHg. Ensure the valve on the Penumbra Aspiration Tubing is switched to the OFF position.
 - 3.7.2 Select the appropriate size Penumbra Separator corresponding to the Penumbra Reperfusion Catheter (see **Table 6** below).

Table 6 – Separator/Reperfusion Catheter Device Size Selection

Vessel Size (mm)	Penumbra Reperfusion Catheter	Penumbra Separator
< 2.0	026	026
2.0 to 3.0	032/3MAX	032/3MAX
3.0 to 4.0	041/4MAX	041/4MAX
> 4.0	054/5MAX	054/5MAX

[figure not shown]
- 3.7.3 Advance the Penumbra Reperfusion Catheter to gently embed the distal tip into the thrombus. **Note: Access to the site of occlusion may be aided by the triaxial use of a compatible inner microcatheter.**
- 3.7.4 Using the introducer sheath provided, insert the Penumbra Separator through the rotating hemostasis valve and into the proximal hub of the Penumbra Reperfusion Catheter.
- 3.7.5 Connect the Penumbra Aspiration Tubing to the side port of the rotating hemostasis valve as shown in **Figure 4** below.

Figure 4 – Assembled Aspiration System with Penumbra Separator

3.7.6 To begin aspiration, open the valve on the Penumbra Aspiration Tubing to the ON position, and advance/retract the Penumbra Separator to assist with aspiration and removal of the thrombus as shown in **Figure 5**.

FIGURE 5. Penumbra Separator and Reperfusion Catheter in Position

- 3.7.7 To stop aspiration, switch the valve on the Penumbra Aspiration Tubing to the OFF position, and turn off the Aspiration Pump.
- 3.7.8 Remove the Penumbra Separator.
- 3.7.9 If necessary, additional Penumbra Separators and Reperfusion Catheters may be used to further remove thrombus at the discretion of the investigator.
- 3.7.10 Using a 5cc or 10cc syringe, aspirate approximately 5cc of blood from the Penumbra Reperfusion Catheter to remove any thrombus that may remain in the catheter.
- 3.7.11 Obtain a post-treatment angiogram by injecting contrast media through the guide catheter.

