Since the approval and launch of the Reperfusion Catheter and Separator 054, a new Penumbra system MAX has been developed to maximize aspiration efficiency for smaller Reperfusion Catheters as well. Reperfusion Catheter 4MAX and 3MAX are designed to navigate more distally and efficiently to aspirate clot. The specifications of the Reperfusion Catheter and Separator 054 remained unchanged but are now being marketed as 5MAX (Table 1). The new Reperfusion Catheter 4MAX and 3MAX are similar in design to the Reperfusion Catheter 5MAX (054). The difference is the distal section of the Reperfusion Catheter 5MAX is reinforced with stainless steel wire and the Reperfusion Catheter 4MAX and 3MAX are reinforced with nitinol wire. Shown below are the specifications of the 5MAX, 4MAX and 3MAX (Tables 1-3).

Table 1 -- Specifications of 5MAX

	5 MAX or 054 Reperfusion Catheter
Distal Inner Diameter	0.054”
Proximal Inner Diameter	0.064”
Distal Outer Diameter	≤ 0.071 ”
Proximal Outer Diameter	≤ 0.083 ”
Effective Length	125.0 \pm 2.0 cm

Table 2 -- Specifications of 4MAX and 041 Reperfusion Catheters

	4MAX Reperfusion Catheter	041 Reperfusion Catheter
Distal Inner Diameter	0.041”	0.041”
Proximal Inner Diameter	0.064”	0.041”
Distal Outer Diameter	≤ 0.058 ”	≤ 0.056 ”
Proximal Outer Diameter	≤ 0.083 ”	≤ 0.056 ”
Effective Length	139.0 \pm 2.0 cm	137.0 \pm 2.0 cm

Table 3 -- Specifications of 3MAX and 032 Reperfusion Catheters

	3MAX Reperfusion Catheter	032 Reperfusion Catheter
Distal Inner Diameter	0.035”	0.032”
Proximal Inner Diameter	0.043”	0.041”
Distal Outer Diameter	≤ 0.052”	≤ 0.047”
Proximal Outer Diameter	≤ 0.063”	≤ 0.047”
Effective Length	153.0 ± 2.0 cm	150.0 ± 2.0 cm

The Separator 3D is another component of the current Penumbra System with an identical indication. It is a self-expanding 3 dimensional, binary Nitinol device that exhibits uniaxial stress-strain characteristics of superelastic Nitinol (**Figure 1**). The specifications of the Separator-3D are shown in **Table 4** below.

Figure 1 -- The Penumbra Separator 3D Device

[figure not shown]

Table 4—Separator 3D Device Specifications

	Wire Distal OD	Tip Diameter (Unconstrained)	Tip Length	Core Wire Flexible Length	Working Length
Separator 3D	0.014” Max	4.6-5.4 mm	26 mm	42 cm	142 cm

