The Separator 3D is an additional Separator with a new tip configuration for the Penumbra System. The Penumbra System's fundamental mechanism of action is aspiration. Aspiration draws clot into the catheter to remove the clot from the body. All Separators function to break up the clot inside of the catheter to make it more amenable to removal from the body via aspiration. The current Separators function by shearing portions of the clot via a small gap between the outer diameter of the Separator cone and the inner diameter of the Reperfusion Catheter while cycling the Separator. The Separator 3D is designed to break up the clot in a 3rd radial dimension as the open body of the Separator 3D is compressed and then retrieved into the Penumbra Reperfusion Catheter. The Separator 3D is attached to the same core wire, and is delivered in the same manner as the current Separators. The tip has an open-body, three-dimensional lattice design. Like the current Separators, aspiration applied during use of the Separator 3D removes the clot from the body. The Separator 3D is compatible with Reperfusion Catheters that have a distal inner diameter of 0.041” or larger. A schematic description

of the functionality of the Separator-3D device with the Reperfusion Catheter is shown in **Figure 3** (Section 3.6.7).

The purpose of this study is to assess the safety and effectiveness of the Separator 3D as a component of the Penumbra System in the revascularization of large vessel occlusion (≥ 2.5 mm in diameter) in acute ischemic stroke.

2. Study Overview

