2.3.1 Inclusion Criteria

- From 18 to 85 years of age
- Present with symptoms consistent with an acute ischemic stroke for revascularization within 8 hours from symptom onset
- Refractory to or not eligible for IV rtPA therapy, e.g., presenting between 0 and 3 hours from symptom onset AND contraindicated for IV rtPA, or presenting between 3 and 8 hours of symptom onset, or evidence from vascular imaging of persistent occlusion after IV rtPA
- Evidence of a large vessel (≥ 2.5 mm in diameter) occlusion in the cerebral circulation
- NIH Stroke Scale (NIHSS) score ≥ 8
- Signed informed consent

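### The first row of Protocol Table 5 pairs the Separator 3D with 032/3MAX catheters, which are below the 0.041 inch compatibility limit stated in Protocol Section 1

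*Protocol*

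**What the plan says.** Section 1 of the Protocol (Introduction) sets the limit: "The Separator 3D is compatible with Reperfusion Catheters that have a distal inner diameter of 0.041" inch or larger. Section 3.6.3 then says "Penumbra Separator 3D is offered in one size and is designed to fit into the listed Penumbra Reperfusion Catheters" and refers to Table 5. The first row of Table 5 gives 032/3MAX for vessels of 2.5 to 3.0 mm. The dimensions of those catheters are in Table 3, "Specifications of 3MAX and 032 Reperfusion Catheters".

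These vessels are in the trial. Section 2.3.1 requires "Evidence of a large vessel (≥ 2.5 mm in diameter) occlusion in the cerebral circulation".

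Four other provisions bear on the point:

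- Section 3.3 (Enrollment) fixes the order of events: "advance the Penumbra Reperfusion Catheter into the occluded target vessel and the patient will be randomized".
- Section 3.4 lets other system components follow the Separator 3D, with one restriction: "The exception is the use of the 054 or 041 separators in the Separator 3D arm". Such use counts as a protocol deviation.
- The note to Section 3.6.4 allows another delivery route: "Access to the site of occlusion may be aided by the triaxial use of a compatible inner microcatheter of 0.025" inch inner diameter or greater.
- Table 6 in Section 3.7, "Separator/Reperfusion Catheter Device Size Selection", covers the standard Separator. It gives 032/3MAX for vessels of 2.0 to 3.0 mm and does not mention the Separator 3D.

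**The concern.** Table 5 is the sizing instruction for the component under test, and one of its three rows points to catheters that Section 1 excludes. A site cannot satisfy both statements in a 2.5 to 3.0 mm vessel.

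The order of events in Section 3.3 makes this a practical matter. The catheter is already in the target vessel when the arm is drawn. If the site sized it from Table 5 and the patient is assigned to the 3D arm, three courses are open:

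1. Use the Separator 3D through a catheter below the stated limit.
2. Exchange the catheter during an acute stroke procedure.
3. Treat without the Separator 3D.

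The first two change how the study device is used in a trial whose primary safety endpoint is device- or procedure-related serious adverse events within 24 hours. The third removes the patient from the per-protocol set, which SAP 5.1 limits to patients who received their assigned treatment and had no major violation. SAP 9.1 makes that set primary for effectiveness, and the loss would fall on the 3D arm only.

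**Working it through.** The plan gives no figure of its own on this point. The sample-size calculation (103 per group, 115 after attrition) is not involved.

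**Step 1: diameters against the limit.** Limit from Section 1: 0.041 inch. Catheter distal inner diameters from Tables 1 to 3. Difference = diameter − 0.041; percentage = difference / 0.041.

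| Table 5 vessel row | Catheter | Distal inner diameter (inch) | Difference (inch) | Meets limit |
|---|---|---|---|---|
| 2.5 to 3.0 mm | 032 | 0.032 | −0.009 (−22.0%) | No |
| 2.5 to 3.0 mm | 3MAX | 0.035 | −0.006 (−14.6%) | No |
| 3.0 to 4.0 mm | 041, 4MAX | 0.041 | 0 | Yes, exactly |
| over 4.0 mm | 054/5MAX | 0.054 | +0.013 (+31.7%) | Yes |

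One row of three conflicts with the limit, and both of its catheters fail.

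**Step 2: which statement is more likely wrong.** Two details bear on this, neither conclusively.

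*Separators restricted in the 3D arm.* Section 3.4 restricts the 041 and 054 separators but not the 026 or 032. That fits a device meant for catheters of 0.041 inch and up.

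*Length.* Table 4 gives the Separator 3D a working length of 142 cm and a tip of 26 mm (2.6 cm). It does not say whether the working length includes the tip. The length projecting beyond the catheter is 142 − L if it does (reading A), and 142 + 2.6 − L = 144.6 − L if it does not (reading B). L is the effective length with its tolerance from Tables 1 to 3.

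| Catheter | L (cm) | Reading A (cm) | Reading B (cm) |
|---|---|---|---|
| 032 | 148 to 152 | −10 to −6 | −7.4 to −3.4 |
| 3MAX | 151 to 155 | −13 to −9 | −10.4 to −6.4 |
| 041 | 135 to 139 | +3 to +7 | +5.6 to +9.6 |
| 4MAX | 137 to 141 | +1 to +5 | +3.6 to +7.6 |
| 5MAX | 123 to 127 | +15 to +19 | +17.6 to +21.6 |

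The 032 and 3MAX are too long on either reading. The check has a limit of its own. On reading A the whole tip emerges only if L is at most 142 − 2.6 = 139.4 cm, which a 4MAX at the upper end of its tolerance exceeds. Because the term is undefined, length supports the finding but does not settle it.

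**Step 3: how many patients.** This needs the share of target vessels between 2.5 and 3.0 mm, and the share of 3D patients among them who are treated without the device. The documents give neither, so no count, power loss or bias can be computed.

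**The case against.** The best defence is that Table 5 does not control. Section 2.5 presents it as a recommendation, and Sections 3.4 and 3.5.1 defer to the Instructions for Use, which this review does not have. Section 3.3 cites neither sizing table. Two roll-in cases per center and sponsor training (Section 6.1) may also bring the conflict to light. All of this may reduce the practical effect, but none of it corrects the protocol text. Section 3.6.3 still states as a design fact that the device fits the catheters listed.

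The triaxial note is a second defence: the device can evidently be delivered through a lumen narrower than 0.041 inch. This does bar one stronger reading. A reader might infer that the Separator 3D cannot physically be used with 032/3MAX, but the documents do not say what sets the limit and do not show that. The note does not remove the conflict. Section 1 states the limit for the Reperfusion Catheter, and Sections 1 and 2.5 say the device is retrieved into that catheter.

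Figures are missing on both sides of Table 5, and text is missing around 3.6.6 and 3.6.7. Something there may qualify the table, but the conflicting sentences and the table row are intact.

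A reader might also infer that any correction must change Table 6. It need not: Table 6 never pairs a catheter with the Separator 3D and conflicts with nothing. It matters only if Table 5 is changed to a larger catheter, because the pre-randomisation choice would then differ between the two tables.

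**Conclusion.** Wrong as written. Section 1 and the first row of Table 5 contradict each other for eligible 2.5 to 3.0 mm vessels, with listed catheters 0.009 inch (22%) and 0.006 inch (15%) below the stated limit. This rests on direct comparison of the protocol's own entries and needs no assumption. That Table 5 is the faulty statement is the likelier reading but is not established. It depends on the device specification and the Instructions for Use.

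The effect on the trial is not quantified and may be small. Of the three courses open to a site, only omitting the device necessarily takes a patient out of the per-protocol set. A reader might infer a loss of power or a biased non-inferiority test, but the documents give no frequencies to support either. Nor do they support the inference that correcting Table 5 alone would leave 3D patients with wider catheters than controls. The catheter is chosen before the arm is known, so such a difference would need exchanges after randomisation, and their frequency is unknown.

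The correction is still worth making. It is cheap, and it concerns safe use of the study device and delivery of the assigned treatment.

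**What to change.** Check the 0.041 inch limit against the device specification and the Instructions for Use, then take one of two routes.

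**If 0.041 inch is correct:**

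- Remove 032/3MAX from Table 5.
- State which compatible catheter applies to 2.5 to 3.0 mm vessels: 041/4MAX, if the Instructions for Use allow it there.
- Require in Section 3.3 that the catheter placed before randomisation is compatible with the Separator 3D. The arm is not yet known, so this covers every patient.
- Under this route only, check that Table 6 leads to the same pre-randomisation catheter in these vessels.

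**If Table 5 is correct:** correct the limit in Section 1. Table 6 stays as it is.

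Notify sites in either case.

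The minimum cost is a protocol clarification and a site notice. The first route also changes catheter choice in 2.5 to 3.0 mm vessels, for controls as well. It has a side effect in the 3D arm: Table 6 matches the 041/4MAX catheter with the 041/4MAX separator, and Section 3.4 makes the 041 separator a deviation there. If the Instructions for Use do not allow 041/4MAX below 3.0 mm, whether to keep those vessels eligible is a trade-off for the sponsor. Raising the vessel-size criterion would shrink the eligible pool by an unknown share and is not required to remove the contradiction.
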